4.4.3. Method of Assigning Subjects to Study Arms (Randomization)

Enrollment/randomization will be performed through the enrollment module in the electronic data capture system maintained by the Statistical and Data Coordinating Center (SDCC).

Eligible subjects will be stratified by clinical site and prior receipt of licensed, seasonal influenza vaccine (defined as receipt of at least one of the 2017/2018 and/or 2018/2019 influenza vaccines) and randomly assigned with allocation (1:1:1:1:1:1) to one of 6 study arms indicated in [Table 1](#). The treatment sequence was generated using permuted block randomization to provide an approximately balanced allocation to the study arms during the study.

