6.3.2. Modified Intention-to-Treat (mITT) Population

The modified intent-to-treat (mITT) population includes all randomized subjects who received the first study vaccination and contributed at least one post-first study vaccination venous blood samples for immunogenicity testing (HAI, NAI or Neut antibody assays) for which valid results were reported. For analyses using the mITT population, subjects will be grouped based on randomized study arm.

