6.3.3. Per Protocol Population

The per protocol (PP) population includes all subjects in the mITT with the following exclusions:

- Data from all available visits for subjects found to be ineligible at baseline.
- Data from all visits for subjects that did not contribute venous blood samples for immunogenicity testing (HAI, NAI or Neut antibody assays) at baseline (Day 1).
- Data from all visits subsequent to major protocol deviations or events, in the opinion of the principal investigator and DMID scientific lead, expected to impact immune response such as:
 - Receipt of non-study licensed live vaccine within 30 days before or after study vaccination,
 - Receipt of non-study licensed inactivated vaccine within 14 days before or after study vaccination,
 - Receipt of immunosuppressive therapy (e.g., corticosteroids) within 30 days before or after the first study vaccination.
- Data from any visit that occurs out of window by more than one day:
 - Visit 2 data collected before Day 2 or after Day 4 post study vaccination.
 - Visit 3 data collected before Day 6 or after Day 10 post study vaccination.
 - Visit 4 data collected before Day 26 or after Day 32 post study vaccination.

- Visit 5 data collected before Day 53 or after Day 61 post study vaccination
- Visit 6 data collected before Day 75 or after Day 105 post study vaccination.
- Visit 7 data collected before Day 114 or after Day 122 post study vaccination.
- Visit 8 data collected before Day 165 or after Day 195 post study vaccination.
- Visit 9 data collected before Day 350 or after Day 401 post study vaccination.

For analyses using the PP population, subjects will be grouped based on study vaccinations received.

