6.5. Missing Data

All attempts will be made to collect all data per protocol. As missing data are expected to be minimal, no imputation will be performed for missing values. Any data point that appears to be erroneous or inexplicable based on clinical judgment will be investigated as a possible outlier. If data points are identified as outliers, sensitivity analyses will be performed to examine the impact of including or excluding the outliers. Any such analysis will be reported and substantive differences will be described.

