8. IMMUNOGENICITY EVALUATION

Immunogenicity data summaries and analysis for primary and secondary endpoints will be presented for the mITT and PP populations. Immune responses in terms of strain-specific 2018/2019, 2019/2020 QIV HAI, NAI, and Neut antibody titers will be summarized by study arm at each time point. Descriptive summary statistics will be provided for all assays and time points including number of subjects with non-missing results, percentage of subjects with titers $\geq 1:40$ for HAI and Neut only, percentage of subjects achieving seroconversion, GMTs along with corresponding 95% CI, and GMFRs along with corresponding 95% CI. Exact confidence intervals using the Clopper Pearson method will be presented for proportional endpoints. Ratios of GMTs along with their 95% CIs between adjuvanted and unadjuvanted groups will be presented at each timepoint. Confidence intervals using the Delta Method will be provided for the ratio of GMTs.

Individual HAI, NAI, and Neut assay results will be provided in [Listing 9](#), [Listing 10](#), and [Listing 11](#). Individual exploratory assay results will be provided in [Listing 12](#), [Listing 13](#), and [Listing 14](#) for memory B cells, [Listing 15](#) for Tfh cells, [Listing 16](#) for plasmablasts, [Listing 17](#) for neutralizing fc-effector, [Listing 18](#) for antibody forensics, and [Listing 19](#) for NA ELISA.

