8.1. Primary Immunogenicity Analysis

The primary immunogenicity endpoints HAI, Neut and NAI seroconversion, percentage of subjects with titer $\geq 1:40$ for HAI and Neut only, GMTs, ratios of GMTs between adjuvanted and unadjuvanted groups, and GMFRs against the 2018/2019 QIV strains 28 days after study vaccination (Day 29) will be summarized as described above. The primary analysis population will be mITT, with results from the PP population providing a comparison of the sensitivity of immunogenicity results to subject adherence to protocol-defined conditions.

Summaries of primary immunogenicity endpoints are presented for the 2018/2019 QIV strains in [Table 21](#), [Table 22](#), [Table 23](#), [Table 24](#), [Table 25](#), [Table 26](#), [Table 27](#), and [Table 28](#) for HAI, [Table 29](#), [Table 30](#), [Table 31](#), [Table 32](#), [Table 33](#), [Table 34](#), [Table 35](#), and [Table 36](#) for Neut, and [Table 53](#), [Table 54](#), [Table 55](#), [Table 56](#), [Table 57](#), [Table 58](#), [Table 59](#), and [Table 60](#) for NAI.

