[Implementation Note: Generate this table for the expedited report and only include Safety Population, modified Intent to Treat and Per Protocol, Day 29).]

Analysis Populations	Reason Subjects Excluded	Group 1 Fluzone (N=X)		Group 2 Fluzone + AF03 (N=X)		Group 3 Fluzone + Advax- CpG (N=X)		Group 4 Flublok (N=X)		Group 5 Flublok + AF03 (N=X)		Group 6 Flublok + Advax- CpG (N=X)		All Subjects (N=X)	
		n	%	n	%	n	%	n	%	n	%	n	%	n	%
Safety Population	Any Reason	x	xx	x	xx	x	xx	x	xx	x	xx	x	xx	x	xx
	Study Dose 1 Not Received														
Modified Intent to Treat	Any Reason														
	Study Dose 1 Not Received														
	No Baseline Results Available														
	No Post-Vaccination Results Available														
Per-Protocol, All Visits	Found to be Ineligible At Baseline														
Per Protocol, Day 8	Any Reason														
	Study Vaccination 1 Not Received														
	No Baseline Results Available														
	No Day 8 Result Reported by Lab														
	Lost to Follow-up Before Day 8														
	Receipt of Non-Study Vaccination														
	Receipt of Immunosuppressive medication														
	Day 8 Visit Out of Window														
Per Protocol, Day 29	Any Reason														

Analysis Populations	Reason Subjects Excluded	Group 1 Fluzone (N=X)		Group 2 Fluzone + AF03 (N=X)		Group 3 Fluzone + Advax- CpG (N=X)		Group 4 Flublok (N=X)		Group 5 Flublok + AF03 (N=X)		Group 6 Flublok + Advax- CpG (N=X)		All Subjects (N=X)	
		n	%	n	%	n	%	n	%	n	%	n	%	n	%
	Study Vaccination 1 Not Received														
	No Baseline Results Available														
	No Day 29 Result Reported by Lab														
	Lost to Follow-up Before Day 29														
	Receipt of Non-Study Vaccination														
	Receipt of Immunosuppressive medication														
	Day 29 Visit Out of Window														
Per Protocol, Day 57	Any Reason														
	Study Vaccination 1 Not Received														
	No Baseline Results Available														
	No Day 57 Result Reported by Lab														
	Lost to Follow-up Before Day 57														
	Receipt of Non-Study Vaccination														
	Receipt of Immunosuppressive medication														
	Day 57 Visit Out of Window														
Per Protocol, Day 90	Any Reason														
	Study Vaccination 1 Not Received														

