GMT (95% CI)	xxx.x (xxx.x,xxx.x)	xxx.x (xxx.x,xxx.x)	xxx.x (xxx.x,xxx.x)	xxx.x (xxx.x,xxx.x)	xxx.x (xxx.x,xxx.x)	xxx.x (xxx.x,xxx.x)	N/A	N/A	N/A	N/A	N/A	N/A
Ratio of GMTs (95% CI) ^a	-	-	xx.x (xx.x,xx.x)	xx.x (xx.x,xx.x)	xx.x (xx.x,xx.x)	xx.x (xx.x,xx.x)	N/A	N/A	N/A	N/A	N/A	N/A

Time Point	Group 1 Fluzone (N=X)		Group 2 Fluzone + AF03 (N=X)		Group 3 Fluzone + Advax-CpG (N=X)		Group 4 Flublok (N=X)		Group 5 Flublok + AF03 (N=X)		Group 6 Flublok + Advax-CpG (N=X)	
	xx (xx, xx)	xx (xx, xx)	xx (xx, xx)	xx (xx, xx)	xx (xx, xx)	xx (xx, xx)	N/A	N/A	N/A	N/A	N/A	N/A
Seroconversion - % (95% CI)	xx (xx, xx)	xx (xx, xx)	xx (xx, xx)	xx (xx, xx)	xx (xx, xx)	xx (xx, xx)	N/A	N/A	N/A	N/A	N/A	N/A
GMFR (95% CI)	xx.x (xx.x,xx.x)	xx.x (xx.x,xx.x)	xx.x (xx.x,xx.x)	xx.x (xx.x,xx.x)	xx.x (xx.x,xx.x)	xx.x (xx.x,xx.x)	N/A	N/A	N/A	N/A	N/A	N/A

N = Number of subjects in the Modified Intent-to-Treat Population; n = Number of subjects with available results; GMT = Geometric Mean Titer; GMFR = Geometric Mean Fold Rise.
*Ratio of GMTs is defined as the ratio of the GMT from the adjuvanted group divided by the GMT from the corresponding unadjuvanted group. Confidence intervals for the ratio of GMTs will use the Delta Method.

Tables with similar format:

- Table 62:** Summaries of Neuraminidase Inhibition Antibody Against 2018/2019 QIV Strain A/Singapore/INFIMH-16-0019/2016 IVR-186 (H3N2) by Study Day, Study Arm, and Baseline Serostatus, Per Protocol Population
- Table 63:** Summaries of Neuraminidase Inhibition Antibody Against 2018/2019 QIV Strain B/Phuket/3073/2013 (B Yamagata lineage) by Study Day, Study Arm, and Baseline Serostatus, Per Protocol Population
- Table 64:** Summaries of Neuraminidase Inhibition Antibody Against 2018/2019 QIV Strain B/Maryland/15/2016 BX-69A (B Victoria lineage) by Study Day, Study Arm, and Baseline Serostatus, Per Protocol Population

Table 65: Summaries of Neuraminidase Inhibition Antibody Against 2018/2019 QIV Strain A/Michigan/45/2015 X-275 (H1N1) by Study Day, Study Arm, and Previous Vaccination, Per Protocol Population

[Implementation Note: NAI titers are only assessed for all study groups for Day 1 and Day 29 and assessed for study groups 1, 2 and 3 for the rest of the timepoints.]

Time Point	Group 1 Fluzone (N=X)		Group 2 Fluzone + AF03 (N=X)		Group 3 Fluzone + Advax-CpG (N=X)		Group 4 Flublok (N=X)		Group 5 Flublok + AF03 (N=X)		Group 6 Flublok + Advax-CpG (N=X)	

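### The Day 29 adjuvanted/unadjuvanted GMT ratio is valid but crude: leaving out Day 1 titre gives up precision that data already collected could supply

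*SAP*

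**What the plan says.** SAP section 8 states that "Ratios of GMTs along with their 95% CIs between adjuvanted and unadjuvanted groups will be presented at each timepoint". The footnote to the Table 21 shell gives the estimator: "Ratio of GMTs is defined as the ratio of the GMT from the adjuvanted group divided by the GMT from the corresponding unadjuvanted group". The interval is by the delta method. No model or covariate is named there, in SAP 8.1 or in Protocol 11.6.3. SAP 6.4 carries the word covariates in its title but lists only exploratory subgroups.

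Two baseline variables are available. SAP 3.2 uses the Day 1 titre to compute fold rise. SAP 4.4.3 says "Eligible subjects will be stratified by clinical site and prior receipt of licensed, seasonal influenza vaccine".

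On the population, SAP 8.1 says "The primary analysis population will be mITT". SAP 6.3.2 admits a vaccinated subject who "contributed at least one post-first study vaccination venous blood samples for immunogenicity testing" with a valid result, and does not ask for a Day 1 result. A missing Day 1 sample appears in SAP 6.3.3 as a per protocol exclusion: "Data from all visits for subjects that did not contribute venous blood samples for immunogenicity testing" at baseline. Yet the Table 12 shell lists "No Baseline Results Available" among the reasons for exclusion from mITT. SAP 6.5 adds that "no imputation will be performed for missing values".

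**The concern.** Protocol 11.1 says the arms are there to evaluate whether each adjuvant enhances the response, and Protocol 11.2 describes the aim as estimation. The GMT ratio is the plan's only numerical between-arm immunogenicity estimate, from about 38 subjects per arm, so its interval width matters. A pre-vaccination titre to the same strain in the same assay is an obvious covariate, and it is not used.

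The other planned outputs do not fill the gap. The Day 1 ratios and per-arm GMFRs in the same tables show a baseline imbalance, but they are not an adjusted comparison of arms with an interval. The ratios by serostatus and prior vaccination are exploratory and restricted to the PP population (SAP 6.4, 8.3), whereas the primary population is mITT.

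An adjusted ratio needs a Day 1 result for every subject it uses. The disagreement between SAP 6.3.2 and the Table 12 shell therefore has to be settled, and it leaves the crude analysis set ambiguous as well.

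**Working it through.** **The plan's own figures.** The documents give no precision figure for the GMT ratio. The nearest is Protocol Table 12: a minimum detectable difference of 0.30 at a comparator proportion of 0.50 and 38 per group. An exact calculation of the likelihood ratio test reproduces it (power 0.800), but it concerns proportions and says nothing about the width of a ratio.

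**Inputs.**
- n = 38 per arm (Protocol 11.4.2; 40 × 0.97 = 38.8).
- SD of ln titre: not given. Assumed 1.2, range 1.0 to 1.5, equal at Day 1 and Day 29.
- Day 1/Day 29 correlation r: not given. Assumed 0.3, 0.5 and 0.7.

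**Formulas for the 95% margin (×/÷), with √(2/38) = 0.2294.**
- Crude: exp(t₇₄ × SD × 0.2294), t₇₄ = 1.9925.
- ANCOVA: exp(t₇₂ × SD × √(1−r²) × 0.2294), t₇₂ = 1.9935.
- Ratio of two arms' GMFRs: exp(t₇₄ × SD × √(2(1−r)) × 0.2294).

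At SD 1.2 the crude margin is exp(1.9925 × 1.2 × 0.2294) = exp(0.5485) = 1.73. At r = 0.5 the adjusted margin is exp(1.9935 × 1.2 × 0.8660 × 0.2294) = exp(0.4753) = 1.61.

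| SD | Crude | Adjusted, r = 0.3 | r = 0.5 | r = 0.7 |
|---|---|---|---|---|
| 1.0 | 1.58 | 1.55 | 1.49 | 1.39 |
| 1.2 | 1.73 | 1.69 | 1.61 | 1.48 |
| 1.5 | 1.99 | 1.92 | 1.81 | 1.63 |

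In sample-size terms, 38/(1−r²) gives about 42, 51 and 75 unadjusted subjects per arm.

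Dividing the reported GMFRs is no substitute. At SD 1.2 that margin is 1.91, 1.73 and 1.53, which is worse than the crude ratio when r is below 0.5 and wider than ANCOVA at every r shown.

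**Simulation of the stratified design.** 10,000 trials per setting; 240 subjects, six arms, eight sites; permuted blocks within site by prior vaccination; 5% loss to leave 38 per arm. Assumptions not in the documents: blocks of 6, half previously vaccinated, Day 1 titre 2- or 3-fold higher in that half, SD 1.2.
- Variance cut from Day 1 titre plus stratum: 6–8%, 18–24% and 38–48% at r = 0.3, 0.5 and 0.7.
- On the SAP's 10×2^k scale with below-limit values set to 5 and an assumed Day 1 median of 20: 6%, 20–21% and 42%.
- Coverage of the adjusted interval: 94.6–95.3%.
- Stratum alone: leaving it out makes the crude interval 0–5.5% wider. Once Day 1 titre is in the model, adding the stratum changes the margin by at most 0.04.

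**Missing Day 1 results.** Comparing (1−r²)/(38−m) with 1/38 puts the break-even at m = 38r², or 3.4, 9.5 and 18.6 missing per arm. That is too generous, because it ignores the lost degrees of freedom and the cost of estimating covariate effects. In simulation the variance cut at those points is already about −2.5%, −4% and −10%. At r = 0.3 it reaches zero at roughly 2.5 to 3 missing per arm.

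**The case against.** The strongest case against is that nothing here is wrong. The crude ratio is the measure in Protocol Table 1, the SAP follows the protocol, and Protocol 11.2 and SAP 6.8 say that no formal hypothesis is being tested. No decision rule depends on the interval, and the size of the gain rests on assumed values. All of that stands. It makes the change an improvement to the plan rather than the repair of an error.

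Several limits on scope also stand.
- The stratum adds almost nothing beyond Day 1 titre; it belongs in the model to match the randomisation.
- The model should not be carried into the subgroup tables. Prior vaccination is constant within each column of the prior-vaccination tables, and seronegative Day 1 titres are at most 1:10 by definition (SAP 3.2).
- For heterologous strains the gain may be smaller. If the Day 1 median were 5, with about 72% of titres at the floor, the variance cut falls to about 3%, 13% and 29%.
- Timing matters. SAP 6.6 treats the expedited report as the final analysis of the Day 1 and Day 29 data.

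The planned Day 1 ratios, GMFRs and subgroup ratios do answer part of the concern, since they let a reader see baseline influence. They do not give an adjusted between-arm estimate.

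**Conclusion.** The point holds as a loss of precision on a primary outcome. At an assumed ln SD of 1.2 and 38 per arm, the margin could fall from ×/÷1.73 to 1.69, 1.61 or 1.48 at r = 0.3, 0.5 or 0.7. At r = 0.3 the benefit is small and does not survive about 2.5 to 3 missing Day 1 results per arm. At r = 0.5 or above it is worth having. The SD and correlation are assumptions throughout.

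A reader might infer that the crude ratio is biased, or that a chance Day 1 imbalance would invalidate it. The documents do not support that: allocation is randomised, Day 1 imbalance between arms is chance, and the crude interval already allows for it. In a separate check with 38 per arm and 19 per stratum, crude coverage was 0.949 to 0.960. Nor does leaving out the stratum distort the comparison to any practical extent.

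The mismatch between SAP 6.3.2 and the Table 12 shell is a genuine inconsistency, and it needs resolving whether or not the adjusted ratio is added.

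**What to change.** In SAP 8 and 8.1, before the data for the expedited report are unblinded, add an adjusted Day 29 ratio beside each crude one against the 2018/2019 strains. Confine it to the main mITT and PP tables (21–36 and 53–60). Obtain it from ANCOVA on ln titre with arm, Day 1 ln titre to the same strain and assay, and prior-vaccination stratum, and back-transform the adjusted difference and its t-based 95% CI. Keep the crude ratio as the Protocol Table 1 measure, and keep sites pooled as in SAP 6.7. The documents do not show whether the expedited report has been issued; if unblinding has already happened, label the adjusted ratio as added afterwards.

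State that mITT subjects without a Day 1 result stay in the crude ratio and are left out of the ANCOVA, and report their number per arm. Amend the Table 12 mITT rows to agree with SAP 6.3.2 under that rule.

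Extension to other time points and heterologous strains is optional. Day 118 ratios should not be adjusted for the Day 90 titre, which is measured after randomisation and after the adjuvanted dose.

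The cost is SAP wording, one standard SAS model and one extra row in each of 24 tables (16 + 8), plus the exclusion counts. Extending to all seven post-vaccination time points, with the 30 heterologous tables, would mean 54 × 7 = 378 rows. No new data or visits are needed.

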4.5.2. Immunogenicity Variables

Individual HAI assay results against the 2018/2019 QIV strains, 2019/2020 QIV strains, and heterologous H3 influenza strains (A/Kenya/105/2017 [H3N2], A/Louisiana/13/2017 [H3N2], A/Aksaray/4048/2016 [H3N2], A/Shandonglaicheng/1763/2016 [H3N2], and A/Michigan/84/2016 [H3N2]) will be performed at Q2 Solution laboratory under the responsibility of GCI and results will be reported by GCI.

Individual Neut assay results will be performed and reported by Global Clinical Immunology (GCI) lab at Sanofi Pasteur laboratory for the 2018/2019 QIV strains, 2019/2020 QIV strains, and heterologous H3 influenza strains (A/Kenya/105/2017 [H3N2], A/Louisiana/13/2017 [H3N2], A/Aksaray/4048/2016 [H3N2], A/Shandonglaicheng/1763/2016 [H3N2], and A/Michigan/84/2016 [H3N2]).

Individual NAI results against the 2019/2020 QIV strains, 2018/2019 QIV strains, and heterologous N1 and N2 NA antigens (A/OMAN/5532/2017, A/CAMEROON/9766/2017, A/Human/Hubei/3/2005, A/LOUISIANA/13/2017, A/TOWNSVILLE/51/2016, A/AKSARAY/4048/2016) will be performed by Q2 Solution laboratory under the responsibility of GCI and the data will be reported by GCI.

HAI, NAI, and Neut assay results are reported as a reciprocal titer with values of 10×2^k , where $k=0, 1, 2$, etc. The lower limit of detection for the HAI, NAI and Neut assays is 1:10; values below the limit of detection are reported as '<10', and for analysis are imputed as one-half the limit of detection ($10/2 = 5$). The upper limit of quantitation (ULOQ) varies by assay and strain. Values above the upper limit of quantitation will be reported as ' \geq ULOQ', and for analysis are imputed as the upper limit of quantitation (ULOQ). HAI, NAI, and Neut

assays will be done in duplicates. Both titers will be reported for the HAI and NAI assays, but only one Geometric Mean Titer (GMT) will be reported for Neut assay. For analysis of HAI and NAI, the geometric mean (calculated on natural log scale) of repeated results for each sample will be computed and used as the response for all subsequent calculations. The variation arising from multiple measurements for an individual at a single time point is not used in subsequent calculations. See Section 3.2 for definitions of derived variables for the analysis of HAI, NAI, and Neut data.

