5. SAMPLE SIZE CONSIDERATIONS

This study is planned to enroll a total of 40 subjects in each group. This study is not designed to test a formal null hypothesis. Rather, it is intended to obtain sufficient data to obtain meaningful estimates of the immune response and to uncover any safety issues that occur at a sufficiently high rate that they might be observed in a study of this size. As such, the type one error rate, $\alpha = 0.05$, is not adjusted for multiple comparisons. While this study is not designed to test any specific null hypothesis, the following tables illustrate the precision and power that is available for select estimates and comparisons of interest.

[Table 3](#) indicates the probability of observing one or more safety events, such as solicited injection site or systemic reactogenicity events or an unsolicited non-serious AE of a particular type for sentinel subjects (N=4 or 6), for a single adjuvanted/ unadjuvanted study arm/stratum (N = 40 or 60), for all subjects receiving the same seasonal QIV (N= 120), for all subjects in the trial (N=240).

Binomial confidence intervals (CI) are widest (have the least precision) when the response rate is 50%.

[Table 4](#) is presented to indicate the worst-case scenario for precision of observed exact (Clopper-Pearson) binomial confidence intervals.

[Table 5](#) illustrates the minimum detectable differences in the proportion of subjects responding (e.g., attaining seroconversion or a titer $\geq 1:40$) between two adjuvanted study arms using a two-sided Likelihood Ratio Test and $\alpha = 0.05$.

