6.2. Timing of Analyses

6.2.1. Expedited Report

Clinical, safety, and reactogenicity data through approximately 56 days after study vaccination will represent the interim clinical database for this trial. Once the last subject completes the visit that occurs approximately 56 days after first study vaccination, the interim clinical database will be cleaned, monitored, and locked. Upon receipt of immunogenicity data for Day 1 and Day 29 (HAI, NAI, and Neut against 2018/2019 QIV strains and heterologous strains) and safety data through Day 57, the sponsor will authorize the SDCC to transfer to Sanofi Pasteur a copy of this unblinded data set. An Expedited Report containing analyses of safety data through Day 57 and HAI, NAI, and Neut data for 2018/2019 QIV strains from baseline (Day 1) and Day 29 unblinded by study arm only will be prepared by the SDCC. These analyses may be made available to the sponsor and pharmaceutical partners for planning subsequent trials as well as to the DSMB for review.

The analyses performed for the Expedited Report or using the data set provided to Sanofi Pasteur will not be used to make any decisions concerning the conduct of this trial. As it is anticipated that subjects will remain in long term safety follow-up at the time of these analyses, blinded investigators and DMID medical monitors not involved in the analysis, publication, or Expedited Report preparation will be responsible for assessing SAEs and AESIs (including Protocol Specified AESIs, MAAEs, NOCMCs and PIMMCs) until all subjects have completed the final follow-up visit.

Tables to be included in the Expedited Report are indicated with the symbol * in the title in [Appendix 1](#).

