8.2. Secondary Immunogenicity Analyses

The secondary immunogenicity endpoints HAI, Neut and NAI seroconversion, percentage of subjects with titer $\geq 1:40$ for HAI, GMFRs, GMTs, and ratios of GMTs (between adjuvanted group and unadjuvanted) against the 2019/2020 QIV strains 28 days after vaccination with the 2019/2020 QIV (Day 118) will be summarized as described above. HAI and Neut seroconversion, percentage of subjects with HAI titers $\geq 1:40$, GMFRs, GMTs, and ratios of GMTs for HAI and Neut against heterologous influenza A/H3 strains on approximately Days 8, 29, 57, 90, and 118 after study vaccination with the 2018/2019 QIV will be also presented. HAI, Neut and NAI seroconversion, percentage of subjects with HAI and Neut titers $\geq 1:40$, and GMTs against the 2018/2019 QIV strains on approximately Days 8, 29, 57, 90, and 118 after study vaccination will be presented. HAI, Neut, and NAI GMFRs against the 2018/2019 QIV strains on approximately Day 57 and Day 90 will also be presented. NAI seroconversion, NAI GMTs and ratios of NAI GMTs against heterologous N1 and N2 NA antigens will also be assessed on approximately Days 8, 29, 57, 90, and 118 for study groups 1, 2 and 3. No formal hypothesis testing is planned.

Secondary summaries for the 2019/2020 QIV strains are provided in [Table 69](#), [Table 70](#), [Table 71](#), [Table 72](#), [Table 73](#), [Table 74](#), [Table 75](#), [Table 76](#), [Table 77](#), [Table 78](#), [Table 79](#), and [Table 80](#). Summaries of HAI, and Neut against heterologous H3 Influenza strains for both mITT and PP populations will also be provided in [Table 81](#), [Table 82](#), [Table 83](#), [Table 84](#), [Table 85](#), [Table 86](#), [Table 87](#), [Table 88](#), [Table 89](#), and [Table 90](#) for HAI, and [Table 91](#), [Table 92](#), [Table 93](#), [Table 94](#), [Table 95](#), [Table 96](#), [Table 97](#), and [Table 98](#) for Neut. Summaries of NAI against heterologous N1 and N2 antigens will be presented in [Table 99](#), [Table 100](#), [Table 101](#), [Table 102](#), [Table 103](#), [Table 104](#), [Table 105](#), [Table 106](#), [Table 107](#), [Table 108](#), [Table 109](#), and [Table 110](#).

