14.2 Efficacy/Immunogenicity Data

Table 21: Summaries of Hemagglutination Inhibition Antibody Against 2018/2019 QIV Strain A/Michigan/45/2015 X-275 (H1N1) by Study Day and Study Arm, Modified Intent-to-Treat Population^{*y}

[Implementation Note: This table will be generated for the expedited report to include only results for Day 1 and Day 29]

Time Point	Group 1 Fluzone (N=X)	Group 2 Fluzone + AF03 (N=X)	Group 3 Fluzone + Advax- CpG (N=X)	Group 4 Flublok (N=X)	Group 5 Flublok + AF03 (N=X)	Group 6 Flublok + Advax- CpG (N=X)
Day 1 (Pre-Vaccination 1)						
n	x	x	x	x	x	x
GMT (95% CI)	xxx.x (xxx.x,xxx.x)	xxx.x (xxx.x,xxx.x)	xxx.x (xxx.x,xxx.x)	xxx.x (xxx.x,xxx.x)	xxx.x (xxx.x,xxx.x)	xxx.x (xxx.x,xxx.x)
Ratio of GMTs (95% CI) ^a	-	xx.x (xx.x,xx.x)	xx.x (xx.x,xx.x)	-	xx.x (xx.x,xx.x)	xx.x (xx.x,xx.x)
Titer < 10 - % (95% CI)	xx (xx, xx)	xx (xx, xx)	xx (xx, xx)	xx (xx, xx)	xx (xx, xx)	xx (xx, xx)
Titer ≥ 1:40 - % (95% CI)	xx (xx, xx)	xx (xx, xx)	xx (xx, xx)	xx (xx, xx)	xx (xx, xx)	xx (xx, xx)
Day 8 Post Vaccination 1						
n	x	x	x	x	x	x
GMT (95% CI)	xxx.x (xxx.x,xxx.x)	xxx.x (xxx.x,xxx.x)	xxx.x (xxx.x,xxx.x)	xxx.x (xxx.x,xxx.x)	xxx.x (xxx.x,xxx.x)	xxx.x (xxx.x,xxx.x)
Ratio of GMTs (95% CI) ^a	-	xx.x (xx.x,xx.x)	xx.x (xxx.x,xxx.x)	-	xx.x (xx.x,xx.x)	xx.x (xx.x,xx.x)
Seroconversion - % (95% CI)	xx (xx, xx)	xx (xx, xx)	xx (xx, xx)	xx (xx, xx)	xx (xx, xx)	xx (xx, xx)
Titer ≥ 1:40 - % (95% CI)	xx (xx, xx)	xx (xx, xx)	xx (xx, xx)	xx (xx, xx)	xx (xx, xx)	xx (xx, xx)
GMFR (95% CI)	xx.x (xx.x,xx.x)	xx.x (xx.x,xx.x)	xx.x (xx.x,xx.x)	xx.x (xx.x,xx.x)	xx.x (xx.x,xx.x)	xx.x (xx.x,xx.x)
Day 29 Post Vaccination 1						
n	x	x	x	x	x	x
GMT (95% CI) ^a	xxx.x (xxx.x,xxx.x)	xxx.x (xxx.x,xxx.x)	xxx.x (xxx.x,xxx.x)	xxx.x (xxx.x,xxx.x)	xxx.x (xxx.x,xxx.x)	xxx.x (xxx.x,xxx.x)
Ratio of GMTs (95% CI) ^a	-	xx.x (xx.x,xx.x)	xx.x (xx.x,xx.x)	-	xx.x (xx.x,xx.x)	xx.x (xx.x,xx.x)
Seroconversion - % (95% CI)	xx (xx, xx)	xx (xx, xx)	xx (xx, xx)	xx (xx, xx)	xx (xx, xx)	xx (xx, xx)
Titer ≥ 1:40 - % (95% CI)	xx (xx, xx)	xx (xx, xx)	xx (xx, xx)	xx (xx, xx)	xx (xx, xx)	xx (xx, xx)

Time Point	Group 1 Fluzone (N=X)	Group 2 Fluzone + AF03 (N=X)	Group 3 Fluzone + Advax- CpG (N=X)	Group 4 Flublok (N=X)	Group 5 Flublok + AF03 (N=X)	Group 6 Flublok + Advax- CpG (N=X)
GMFR (95% CI)	xx.x (xx.x,xx.x)	xx.x (xx.x,xx.x)	xx.x (xx.x,xx.x)	xx.x (xx.x,xx.x)	xx.x (xx.x,xx.x)	xx.x (xx.x,xx.x)
Day 57 Post Vaccination 1						
n	x	x	x	x	x	x

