GMFR (95% CI)	xx.x (xx.x,xx.x)	xx.x (xx.x,xx.x)	xx.x (xx.x,xx.x)	xx.x (xx.x,xx.x)	xx.x (xx.x,xx.x)	xx.x (xx.x,xx.x)
Day 365 Post Vaccination 1						
n	x	x	x	x	x	x
GMT (95% CI)	xxx.x (xxx.x,xxx.x)	xxx.x (xxx.x,xxx.x)	xxx.x (xxx.x,xxx.x)	xxx.x (xxx.x,xxx.x)	xxx.x (xxx.x,xxx.x)	xxx.x (xxx.x,xxx.x)
Ratio of GMTs (95% CI) ^a	-	xx.x (xx.x,xx.x)	xx.x (xx.x,xx.x)	-	xx.x (xx.x,xx.x)	xx.x (xx.x,xx.x)
Seroconversion - % (95% CI)	xx (xx, xx)	xx (xx, xx)	xx (xx, xx)	xx (xx, xx)	xx (xx, xx)	xx (xx, xx)
Titer ≥ 1:40 - % (95% CI)	xx (xx, xx)	xx (xx, xx)	xx (xx, xx)	xx (xx, xx)	xx (xx, xx)	xx (xx, xx)
GMFR (95% CI)	xx.x (xx.x,xx.x)	xx.x (xx.x,xx.x)	xx.x (xx.x,xx.x)	xx.x (xx.x,xx.x)	xx.x (xx.x,xx.x)	xx.x (xx.x,xx.x)

N = Number of subjects in the Modified Intent-to-Treat Population; n = Number of subjects with available results; GMT = Geometric Mean Titer; GMFR = Geometric Mean Fold Rise.

^aRatio of GMTs is defined as the ratio of the GMT from the adjuvanted group divided by the GMT from the corresponding unadjuvanted group. Confidence intervals for the ratio of GMTs will use the Delta Method.

Tables with similar format

- Table 22:** Summaries of Hemagglutination Inhibition Antibody Against 2018/2019 QIV Strain A/Singapore/INFIMH-16-0019/2016 IVR-186 (H3N2) by Study Day and Study Arm, Modified Intent-to-Treat Population ^{*¥}
- Table 23:** Summaries of Hemagglutination Inhibition Antibody Against 2018/2019 QIV Strain B/Phuket/3073/2013 (B Yamagata lineage) by Study Day and Study Arm, Modified Intent-to-Treat Population ^{*¥}
- Table 24:** Summaries of Hemagglutination Inhibition Antibody Against 2018/2019 QIV Strain B/Maryland/15/2016 BX-69A (B Victoria lineage) by Study Day and Study Arm, Modified Intent-to-Treat Population ^{*¥}
- Table 25:** Summaries of Hemagglutination Inhibition Antibody Against 2018/2019 QIV Strain A/Michigan/45/2015 X-275 (H1N1) by Study Day and Study Arm, Per Protocol Population ^{*¥}
- Table 26:** Summaries of Hemagglutination Inhibition Antibody Against 2018/2019 QIV Strain A/Singapore/INFIMH-16-0019/2016 IVR-186 (H3N2) by Study Day and Study Arm, Per Protocol Population ^{*¥}
- Table 27:** Summaries of Hemagglutination Inhibition Antibody Against 2018/2019 QIV Strain B/Phuket/3073/2013 (B Yamagata lineage) by Study Day and Study Arm, Per Protocol Population ^{*¥}

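### The SAP gives the primary GMT-ratio confidence interval as a delta-method interval without stating the scale, the quantile or the back-transformation

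*SAP*

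**What the plan says.** The ratio of GMTs between adjuvanted and unadjuvanted arms at Day 29 is a primary outcome for HAI, NAI and Neut (Protocol Table 1; SAP 3.1 and 8.1). SAP Section 8 gives its interval as follows: "Confidence intervals using the Delta Method will be provided for the ratio of GMTs". The footnote to the Table 21 shell, repeated in the other GMT-ratio shells, adds no detail: "Confidence intervals for the ratio of GMTs will use the Delta Method". It does fix the direction: "Ratio of GMTs is defined as the ratio of the GMT from the adjuvanted group divided by the GMT from the corresponding unadjuvanted group".

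Nothing else in either document fills the gap. SAP 4.5.2 mentions a log scale only for averaging replicate assays: "the geometric mean (calculated on natural log scale) of repeated results for each sample will be computed". SAP Section 11 names SAS but no procedure. Protocol 11.6.3 promises 95% intervals without a method. For proportions, the same paragraph of SAP Section 8 does name its method, Clopper-Pearson.

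On purpose and use, SAP Section 5 says of the study that "it is intended to obtain sufficient data to obtain meaningful estimates of the immune response". The Table 21 shell carries the note "This table will be generated for the expedited report to include only results for Day 1 and Day 29", and SAP 6.2.1 says of the expedited report: "These analyses may be made available to the sponsor and pharmaceutical partners for planning subsequent trials".

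**The concern.** A GMT is the exponential of a mean ln titer, so the log of a GMT ratio is a difference of two independent means. Its standard error follows directly, without a delta method. The method is needed only to get a standard error for the ratio on its own scale, which leads to symmetric limits around the ratio. Read literally, the plan therefore points towards a ratio-scale interval, although a log-scale interval loosely called a delta-method interval also fits the words. Two programmers could follow the text and report different primary intervals.

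In the table shells this ratio is the only between-arm immunogenicity contrast with its own interval. At Day 29 in the mITT population there are 4 strains x 3 assays x 4 adjuvant contrasts = 48 of them. In a trial whose stated aim is estimation, the position of the limits is part of the result.

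**Working it through.** The plan states no SD, interval width or power for the GMT ratio, so there is no figure of its own to reproduce.

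**Inputs**
- n per arm: up to 40 for mITT, the primary immunogenicity population (SAP 8.1; 40 enrolled per arm). Protocol 11.4.3 expects 38 for per protocol.
- SD of ln titer: not in the documents. Assumed 0.8, 1.0, 1.25 and 1.5, equal in both arms.
- Quantile q: t with 2n - 2 degrees of freedom, which is 1.9908 for n = 40 and 1.9925 for n = 38.

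**Formulas.** Let R be the observed ratio, s = SD x sqrt(2/n) the standard error of ln R, and x = q x s.
- Ratio-scale delta interval: R(1 - x) to R(1 + x).
- Log-scale interval, exponentiated: R exp(-x) to R exp(x).

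For every x > 0, 1 - x < exp(-x) and 1 + x < exp(x). With the same quantile, both ratio-scale limits are therefore below the log-scale limits whatever the SD or n. If z is used on one scale and t on the other, the order still holds at 38 per arm once the SD exceeds about 0.07.

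**Size of the shift.** For n = 40, sqrt(2/40) = 0.2236, so x = 0.4452 x SD. For n = 38, sqrt(2/38) = 0.2294, so x = 0.4571 x SD. The drop in the lower limit is 1 - (1 - x)/exp(-x); in the upper limit it is 1 - (1 + x)/exp(x).

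| SD | lower limit, n = 40 | upper limit, n = 40 | lower limit, n = 38 | upper limit, n = 38 |
|---|---|---|---|---|
| 0.8 | -8.1% | -5.0% | -8.6% | -5.3% |
| 1.0 | -13.4% | -7.4% | -14.3% | -7.7% |
| 1.25 | -22.6% | -10.8% | -24.1% | -11.3% |
| 1.5 | -35.2% | -14.5% | -37.6% | -15.1% |

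Worked case, n = 40, SD 1.0, observed ratio 2: x = 0.4452. The ratio scale gives 2(0.5548) to 2(1.4452), or 1.11 to 2.89. The log scale gives 2(0.6407) to 2(1.5608), or 1.28 to 3.12.

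**Coverage and tails.** Simulated log-normal titers, 38 per arm, Welch t on both scales:

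| SD | ratio-scale coverage | wholly below truth | wholly above truth |
|---|---|---|---|
| 0.8 | 94.5% | 4.7% | 0.8% |
| 1.0 | 94.2% | 5.2% | 0.5% |
| 1.25 | 93.8% | 6.0% | 0.3% |
| 1.5 | 93.3% | 6.6% | 0.1% |

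The log-scale t interval covers 95.0% with 2.5% on each side, at every SD. With z the log scale covers about 94.6%. Rounding titers to two-fold steps and setting values under 10 to 5 (assumed unadjuvanted GMT 40, true ratio 1) barely changes the ratio-scale coverage: 94.5, 94.1, 94.0 and 93.5%.

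**Negative lower limits** need x > 1, that is an SD above 1/0.4571 = 2.19 at 38 per arm. Within the assumed range they arise only in small subgroup cells, which SAP 6.4 treats as exploratory.

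**The case against.** The main objection is that an under-specified method has been shown, not a wrong interval. A log-scale standard error with exponentiated limits fits the words, and a statistician used to titers might well do exactly that. This stands: on that reading nothing is displaced. The size on the other reading also depends on an SD that the documents do not give, and that too stands.

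Little rests on these limits. SAP 8.2 says "No formal hypothesis testing is planned" for the secondary analyses, and SAP 6.8 says the study tests no specific null hypothesis. SAP 6.2.1 rules out using the expedited report for decisions on the trial's conduct. SAP 6.6.2 does not list the ratio among the interim quantities of focus, although the ratio rows are in the shells marked for that report. Each arm's GMT and GMFR appear with intervals in the same tables, and the manufacturer receives the unblinded data set and can compute an interval on either scale. All of this limits the consequence. It does not supply the missing specification.

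A reader might infer that the primary intervals will be biased against the adjuvants. The direction is right on the ratio-scale reading, because the adjuvanted arm is the numerator. The documents do not establish that reading, and the point estimate is the same on either scale. A reader might also infer a serious loss of coverage. Even on the ratio scale the loss is 0.5 to 1.7 percentage points; the larger effects are the limit positions and the unequal tails.

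**Conclusion.** The omission is real: the interval for a primary outcome is named but not defined, and the name fits most naturally a standard error on the ratio itself. If that is what is done, both limits are too low relative to the log-scale interval. The lower limit is about 8 to 35% lower at 40 per arm and 9 to 38% lower at 38. Coverage at 38 per arm is about 94.5 to 93.3%, with the tails unbalanced. If a log-scale interval is exponentiated, there is no displacement. The order of the limits is algebra; the sizes rest on assumed ln-titer SDs of 0.8 to 1.5 and roughly log-normal titers. The interval is descriptive, so this is a minor point that costs nothing to settle, and it does not show that any result will be biased.

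**What to change.** In SAP Section 8 and in each GMT-ratio table footnote, replace the reference to the delta method with: *The 95% CI is the two-sample t interval (Welch, or pooled if named in advance) for the difference in mean ln titer, adjuvanted minus unadjuvanted, with both limits exponentiated.* The essential parts are the log scale, the stated quantile and the exponentiation; the choice between Welch and pooled is secondary. This costs one sentence and a repeated footnote. It needs no new data and the calculation is no harder. If the work is already planned on the log scale with a t quantile, only the wording changes.
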